Require that participants remain in clinic until the 24-hour postdose PK blood sample is collected (increases in-clinic admission by one night). Also results in change of timing for distribution of alcohol use symptom diary.	To simplify clinical operations and reduce the likelihood of missed sample collection.	1.3. Schedule of Activities
Changed pre-admission alcohol testing from urine to breath.	Breath-alcohol testing provides a more accurate assessment of recent alcohol intake than does urine testing.	1.3. Schedule of Activities 5.3. Lifestyle Considerations 8.6.1. Ethanol Interaction Assessments 10.2. Clinical Laboratory Tests
Added that a positive urine drug screen on Day -1 (in addition to at Screening) will result in study exclusion.	To ensure that participants are not users of illicit drugs.	1.3. Schedule of Activities 5.2. Exclusion Criteria
Updated text in Exclusion Criterion #3 (history of suicidal ideation or behavior).	To provide clarification on the timeframe during which positive answers in the C-SSRS would result in study exclusion.	5.2. Exclusion Criteria

Description of Change	Brief Rationale	Section # and Name
Added that metabolites of DCR-AUD may also be analyzed	To provide for a more complete PK profile of DCR-AUD	8.5 Pharmacokinetics
Changed sampling times for blood draws for ADA detection from Days 29 and 57 to Days 42 and 70.	To provide for ADA sample collection 14 days after each dose administration.	1.3. Schedule of Activities
Changed timing of ALDH2 genotyping from Screening to Day -1.	To allow that only eligible participants undergo genotyping.	1.3. Schedule of Activities

TABLE OF CONTENTS

TITLE PAGE	1
SPONSOR SIGNATURE PAGE	2
MEDICAL MONITOR AND PHARMACOVIGILANCE CONTACT INFORMATION.....	3
PROTOCOL AMENDMENT SUMMARY OF CHANGES.....	4
1. PROTOCOL SUMMARY.....	11
1.1. Synopsis.....	11
1.1.1. Rationale	11
1.1.2. Objectives and Endpoints	12
1.1.3. Overall Design	12
1.2. Overall Study Schema	14
1.3. Schedule of Activities (SoA)	15
2. INTRODUCTION	21
2.1. Study Rationale.....	21
2.1.1. Overview of Alcohol Use Disorder	21
2.1.2. Nonclinical Overview of DCR-AUD	22
2.2. Benefit/Risk Assessment	23
2.2.1. Risks Related to DCR-AUD Mechanism of Action.....	23
2.2.2. Risk Assessment	25
2.2.3. Benefit Assessment.....	26
2.2.4. Overall Benefit:Risk Conclusion.....	26
3. OBJECTIVES AND ENDPOINTS	27
4. STUDY DESIGN	28
4.1. Overall Design	28
4.2. Scientific Rationale for Study Design	28
4.3. Justification for Dose	29

1. PROTOCOL SUMMARY

1.1. Synopsis

Protocol Title: A Phase 1b, Double-blind, Placebo-controlled, Repeat-dose, Safety, Tolerability, Pharmacokinetic, and Pharmacodynamic Study of DCR-AUD in Healthy Volunteers

Short Title: Phase 1b Repeat Dose Study of DCR-AUD in Healthy Volunteers

1.1.1. Rationale

DCR-AUD is being developed for the treatment of alcohol use disorder (AUD) in adults using an RNA interference (RNAi) technology platform. DCR-A1203, the drug substance of DCR-AUD, is a synthetic double-stranded (annealed duplex) RNA oligonucleotide conjugated to GalNAc ligands that enable subcutaneous delivery of stable, highly specific, and long-acting knockdown of mRNA in the liver via hepatic GalNAc carbohydrate receptors. The target of DCR-AUD is aldehyde dehydrogenase 2 (ALDH2), one of the primary enzymes required for alcohol metabolism. Alcohol metabolism occurs predominantly in the liver via a 2-step process in which alcohol is first converted to acetaldehyde via alcohol dehydrogenase and then to acetic acid by ALDH2. ALDH2 enzyme inhibition can result in unpleasant symptoms after alcohol consumption such as flushing, headache, lightheadedness, palpitations, nausea, and vomiting, as a result of unmetabolized acetaldehyde accumulation. Unpleasant reactions to alcohol consumption in humans with naturally occurring *ALDH2* mutations are thought to be protective against AUD and account for its low prevalence in individuals who are heterozygous or homozygous for *ALDH2* allele mutations causing slower metabolism of acetaldehyde. The magnitude and duration of acetaldehyde accumulation is proportional to both the degree of ALDH2 enzyme inhibition (e.g., partial vs total) and the amount of alcohol consumed.

DCR-AUD is designed to selectively reduce *ALDH2* mRNA and ALDH2 activity in the liver, and thereby decrease the conversion of acetaldehyde to acetic acid after ethanol ingestion. In cynomolgus monkeys, a single SC dose of 3 mg/kg DCR-AUD resulted in reduction of *ALDH2* mRNA expression in liver up to 112 days postdose, with maximum reduction observed at 4 weeks postdose.

This repeat-dose study is being conducted to characterize the safety and tolerability and PK profiles of DCR-AUD when administered monthly, and to determine if a PD effect (resulting from cumulative *ALDH2* mRNA knock down) can be observed during Ethanol Interaction Assessments (EIA) in a population of social drinkers after repeat doses of DCR-AUD.

1.1.2. Objectives and Endpoints

Objectives	Endpoints
Primary	
To evaluate the safety and tolerability of repeat doses of DCR-AUD administered to adult HVs	
 Incidence and severity of AEs and SAEs Changes from baseline in vital signs, 12-lead ECG, clinical laboratory tests, and physical examination findings
Secondary	
1. To characterize the PD symptom profile of repeat doses of DCR-AUD in adult HVs	Change in the occurrence and/or severity of 6 symptoms related to plasma acetaldehyde accumulation observed during in-clinic EIAs over the course of the study.
2. To characterize the plasma PD of repeat doses of DCR-AUD	Change in plasma PD biomarker assessments during serial EIA 
 acetaldehyde acetate ethanol
3. To characterize the PK of repeat doses of DCR-AUD in adult HVs	Plasma PK parameters of DCR-AUD
Exploratory	
To explore change in alcohol consumption following treatment with DCR-AUD in adult HVs	
 Change in alcohol consumption from baseline using TLFB Change from baseline in phosphatidylethanol levels

Abbreviations: AE: adverse event; EIA: ethanol interaction assessment; HV: healthy volunteer; PD: pharmacodynamics; PK: pharmacokinetic; SAE: serious adverse event; TLFB: Timeline Follow Back

1.1.3. Overall Design

This is a double-blind, randomized, placebo-controlled study of DCR-AUD to evaluate the safety, tolerability, PK, and PD of repeat doses of DCR-AUD in adult HVs.

Participants will receive 3 injections of study intervention (Day 1, Day 29, and Day 57), and have assessment visits through Week 24. Up to 10 EIAs will be conducted over the 24-week period to characterize the PD of DCR-AUD. For each EIA, participants will consume 4 standard drinks over the course of 80 minutes. Participants will be admitted to the clinic overnight for each EIA. At the discretion of the Investigator, participants who present with increasing positive ethanol reaction symptoms at the Day 169 EIA (flushing, headache, lightheadedness, palpitations, nausea, or vomiting) will be followed for an additional 4 weeks (through Day 197).

Table 1 presents the schedule of activities for the Screening, Dosing, End of Study, and Conditional Follow-up Visits. **Table 2** presents the schedule of activities for interim visits at which no study drug is administered. **Table 3** presents the schedule of activities for the EIA.

Number of Participants:

16 participants are planned for enrollment.

Intervention Groups and Duration:

Participants will be randomized 3 to 1 to DCR-AUD or placebo, administered at a dose of 480 mg once every 4 weeks at Days 1, 29, and 57.

Individual participants will be screened for a period of up to 4 weeks. Randomization and administration of the first dose of study intervention will occur on Day 1. Participants will return to the site for safety, tolerability, PK, and PD monitoring at specified time points as per the Schedule of Activities. Participants will be followed for approximately 24 weeks after the first injection of study intervention.

Study Population Key Criteria:

[figure not shown]
- Overtly healthy men and women aged 21 to 65 years.
- No diagnosis of AUD within the preceding 12 months per Diagnostic and Statistical Manual of Mental Disorders (DSM-5).
- Social drinkers who consume, on average, 5 to 20 drinks per week for men or 5 to 14 drinks per week for women over the 4 weeks prior to screening, and not more than 8 drinks in a single day.
- No evidence of overt or sub-clinical hepatic pathology, as manifest by serologic tests demonstrating hepatic inflammation or compromised hepatic synthetic function.
- No history of substance use disorder (SUD) or illicit drug use (excluding cannabis) within the preceding 12 months.
- No history of alcohol withdrawal symptoms including delirium tremens or alcohol-related seizures.

Treatment Blinding:

Participants and site study staff will be blinded to the randomization. Some members of the Sponsor team will be unblinded. Complete details will be presented in the Study Blinding Plan.

1.2. Overall Study Schema

Figure 1: Study Schematic for DCR-AUD-102

- a. DCR-AUD (480 mg) or placebo administered on Days 1, 29, and 57
- b. 4-Week conditional follow-up (CFU) conducted at the discretion of the Investigator in participants experiencing symptoms at the End-of-Study (Week 24) visit.

1.3. Schedule of Activities (SoA)

Table 1: Schedule of Activities – Screening, Dosing, EOS, and CFU Visits (see Table 2 for non-dosing visits)

	Screen	Dosing Visits						EOS/ET ^a	CFU ^b
		—		4		8			
		Pre	Post	Pre	Post	Pre	Post		
Study Week								24	28
Study Day	-28 to -2	-1	1	2	4	28	29	30	197
Window (days) ^c	—	—	—	—	—	±2	—	—	±7
Procedure/Assessment									
Informed consent	X								
Inclusion/exclusion criteria	X								
Demographic characteristics	X								
General medical history	X								
Medication history	X								
Psychological history	X								
Urine drug testing ^d	X								
Screening laboratory testing ^e	X								
ALDH2 genotyping ^f	X								
MINI Screen	X								
C-SSRS ^g	X	X				X		X	
Alcohol TLFB ^h	X	X			X		X		
Pregnancy test ⁱ	X	X			X		X		X
SARS-CoV-2 test ^j		X			X		X		X
Drug/alcohol screen ^k		X			X		X		X
Clinic site admission ^l		X			X		X		X

Table 1: Schedule of Activities – Screening, Dosing, EOS, and CFU Visits (see Table 2 for non-dosing visits) (Continued)

Procedure/Assessment	Screen	Dosing Visits								EOS/ET ^a	CFU ^b		
		4				8							
		Pre	Post	Pre	Post	Pre	Post	Pre	Post				
Clinic site discharge ^m			X		X		X		X		X		
EIA ⁿ	X			X				X					
Randomize	X									X			
Administer study intervention		X			X				X				
12-lead ECG ^o	X	X	X		X	X		X	X		X		
Vital signs	X ^p	X	X ^q		X	X ^q		X	X ^q		X		
Physical examination ^r	X	X		X			X				X		
Blood sample for PEth ^s	X						X				X		
Hematology, chemistry, UA ^t	X			X			X				X		
Coagulation panel ^u	X			X			X				X		
Complement panel ^v		X	X	X				X	X				
Blood sample for ADA ^w		X									X		
Blood sample for PK ^x		X	X	X		X	X	X	X		X		
Alcohol use symptom diary ^y		X		X		X		X			X		
Record AEs & SAEs ^z	X	X	X	X	X	X	X	X	X		X		
Record concomitant meds	X	X	X	X	X	X	X	X	X		X		

Abbreviations: ADA=antidrug antibody; AE=adverse event; ALDH2=aldehyde dehydrogenase 2 gene; CBC=complete blood count; CFU=conditional follow-up visit;

C-SSRS=Columbia-Suicide Severity Rating Scale; ECG=electrocardiogram; EIA=ethanol interaction assessment; EOS=end of study; ET=early termination;

FSH=follicle-stimulating hormone; HbA1c=hemoglobin A1c; ICF=informed consent form; MINI=Mini-International Neuropsychiatric Interview; PEth=phosphatidylethanol;

PK=pharmacokinetic; RBC=red blood cell; SAE=serious adverse event; SARS-CoV-2=severe acute respiratory syndrome coronavirus 2; SIB=suicidal ideation or behavior;

TLFB=Timeline Follow Back; UA=urinalysis

^a At the time of discontinuation for the study, an early termination (ET) visit should be conducted, if possible.

- ^b Participants with significant symptoms at the Day 168 EIA will be followed for an additional 4 weeks at the discretion of the Investigator.
- ^c Visits without a specified window are to be conducted relative to the associated scheduled visit. For example, Day 28 will always be the day prior to the Day 29 visit, regardless of where Day 29 falls within the \pm 2-day visit window.
- ^d Screening tests positive for cannabis are not exclusionary.
- ^e To include hematology (CBC with differential and RBC indices), clinical chemistry, coagulation panel, urinalysis, viral serology, HbA_{1c}, and FSH (as indicated). See [Section 10.2](#) for a complete list of parameters.
- ^f Baseline genetic testing for *ALDH2* mutations. Participation is optional; participants who do not wish to undergo genotyping may still participate in the study.
- ^g The Baseline version will be administered at Screening and at subsequent visits the “C-SSRS Since Last Visit” version will be administered. Participants who exhibit signs of Suicidal Ideation or Behavior (SIB) should undergo a risk assessment. All factors contributing to SIB should be evaluated and consideration should be given to discontinuation of study intervention.
- ^h TLFB will be completed for the 2-week period that precedes each study visit, including Screening.
- ⁱ Pregnancy testing required only in female participants. If a urine pregnancy test is positive, confirm with serum pregnancy test. Local laboratory may be used. Female participants must have a negative pregnancy test prior to overnight admission.
- ^j Testing to be performed at the site upon admission. Participants with a positive SARS-CoV-2 test will not be admitted to clinic and will not receive study intervention or undergo EIA. Other assessments not requiring clinic admission (i.e., safety assessments) will be performed. Testing will be performed per site standard processes.
- ^k Study participants are to refrain from drinking alcohol and using cannabis for 24 hours prior to each EIA. Participants with a positive urine-drug or breath-alcohol test will not be admitted to clinic and will not undergo EIA. Participants with a positive urine drug test on Day –1 will be excluded from the study.
- ^l Participants must be fasting for at least 3 hours prior to admission to the clinic.
- ^m Participants may be discharged from clinic following collection of the 24-hour postdose PK sample. Participants will return to clinic for collection of PK samples at 72 hours postdose on Days 4 and 32.
- ⁿ EIA will be conducted on the first day of the visit once all other assessments for that day have been completed. A total of 10 EIAs will be conducted. The timing of assessments and ethanol administration are detailed in [Table 3](#).
- ^o On dosing days, ECGs will be conducted approximately 30 minutes predose and 15-to-30 minutes postdose. If multiple assessments are due, the order of assessment should be ECG, vitals, PK, and then other assessments; with PK sample collection occurring at the nominal time. At Screening and EOS, one ECG will be performed. Screening ECGs may be repeated one time for determination of eligibility.
- ^p Blood pressure, if out of range at Screening, may be repeated one time for determination of eligibility.
- ^q Blood pressure and pulse rate to be recorded 15 (\pm 5) minutes postdose.
- ^r Height will be measured and recorded at Screening. Weight will be measured and recorded at every visit.
- ^s Sample to be collected prior to ethanol administration.
- ^t Hematology to include complete blood count with differential and RBC indices. See [Section 10.2](#) for a complete list of parameters.
- ^u See [Section 10.2](#) for a complete list of parameters.
- ^v Blood samples for complement testing to be collected predose and 2, 8, and 24 hours postdose on Day 1 and Day 57.
- ^w Blood sample for ADA testing to be drawn at same time as predose PK sample on Day 1.
- ^x Plasma samples for PK analysis to be collected predose and at 1, 2, 4, 6, 8, 24, and 72 hours postdose (exception: no 72-hour PK sample is required at Day 57). A single sample will be collected on Day 168. If multiple assessments are due, the order of testing should be ECG, vitals, PK, and then other assessments, with the PK sampling performed preferably at the nominal time point. A \pm 15-minute window will be allowed for collections at 1, 2, 4, 6, and 8 hours postdose. A \pm 30-minute window will be allowed for collection at 24 hours postdose. A \pm 60-minute window will be allowed for collection at 72 hours postdose.
- ^y Participants to record any symptoms associated with use of alcohol outside of in-clinic EIAs. Diary to be issued at time of discharge from clinic and collected and reviewed upon return to clinic.
- ^z AEs and SAEs will be recorded from time ICF is signed. SAEs will be followed until resolution, stabilization, the event is otherwise explained, or the participant is lost to follow-up.

Table 2: Schedule of Activities – Non-dosing Visits (see Table 1 for Screening, Dosing, and EOS Visits)

Procedure/Assessment	Week	2	6	10	12	16	20
Study Day	14	15	42	43	70	71	84
Visit Window (days) ^a	–	±2	–	±2	–	±3	–
Drug/alcohol screen ^{b c}	X	X	X	X	X	X	X
Pregnancy test ^d	X	X	X	X	X	X	X
SARS-CoV-2 test ^{e c}	X	X	X	X	X	X	X
Clinical site admission ^f	X	X	X	X	X	X	X
Physical examination ^g	X	X	X	X	X	X	X
C-SSRS ^h					X		
Hematology, chemistry, UA ^{i j}					X		
Coagulation panel ^j					X		
Blood sample for ADA ^k	X	X	X	X			
Blood sample for PK ^k	X	X	X	X			
Blood sample for PEth ^k						X	
EIA ^l	X	X	X	X	X	X	X
Alcohol TLFB ^m	X	X	X	X	X	X	X
Alcohol use symptom diary ⁿ	X	X	X	X	X	X	X
Record AEs and SAEs ^o	X	X	X	X	X	X	X
Record concomitant meds	X	X	X	X	X	X	X
Clinical site discharge ^p	X	X	X	X	X	X	X

Abbreviations: ADA=antidrug antibody; AE=adverse event; C-SSRS=Columbia-Suicide Severity Rating Scale; EIA=ethanol interaction assessment; PEth=phosphatidyl/ethanol; PK=pharmacokinetics; SAE=serious adverse event; SARS-CoV-2=severe acute respiratory syndrome coronavirus 2; SIB=suicidal ideation or behavior; TLFB=Timeline Follow Back; UA=urinalysis

^a Visits without a specified window are to be conducted relative to the associated scheduled visit. For example, Day 14 will always be the day prior to the Day 15 visit, regardless of where Day 15 falls within the \pm 2-day visit window.

^b Study participants are to refrain from drinking alcohol and using cannabis for 24 hours prior to each EIA. Participants with a positive urine-drug or breath-alcohol test will not be admitted to clinic and will not undergo EIA. Other assessments not requiring clinic admission (i.e., safety assessments) should be performed.

^c Other assessments not requiring clinic admission (i.e., safety assessments) should be performed.

^d Pregnancy testing required only in female participants. If a urine pregnancy test is positive, confirm with serum pregnancy test. Local laboratory may be used. Female participants must have a negative pregnancy test prior to overnight admission.

^e Participants with a positive SARS-CoV-2 test will not be admitted to clinic and will not undergo EIA. Testing will be performed per site standard processes.

^f Participants must be fasting for at least 3 hours prior to admission to the clinic.

^g Weight will be measured and recorded at each visit.

^h The “C-SSRS Since Last Visit” version will be administered. Participants who exhibit signs of SIB should undergo a risk assessment.

ⁱ Hematology to include complete blood count.

^j See Section 10.2 for complete list of testing parameters.

^k Sample to be collected prior to ethanol administration for EIA.

^l EIA will be conducted once all other assessments for that day have been completed. The timing of assessments and ethanol administration are detailed in Table 3.

^m TLFB will be completed for the 2-week period that precedes each study visit.

ⁿ Participants to record any symptoms associated with use of alcohol outside of in-clinic EIAs. Diary to be issued at time of discharge from clinic and collected and reviewed upon return to clinic.

^o AEs and SAEs will be recorded from time ICF is signed. SAEs will be followed until resolution, stabilization, the event is otherwise explained, or the participant is lost to follow-up.

^p Participants will be discharged in the morning when the PI deems it medically appropriate to do so.

Table 3: Schedule of Activities - 4-Hour Ethanol Interaction Assessments

		Pre-EIA										EIA Test Period				
	Time (minutes)	-50	-20	0 ^a	20	30	40	60	90	120	150	180	210	240		
	Window (minutes)		-	±5	±5	±5	±5	±10	±10	±10	±10	±10	±10	±10	±10	
Procedure:																
Standard meal ^b	X															
Venous catheter placement ^c		X														
12-lead ECG ^d		X						X							X	
Vital signs ^{d,e}		X	X			X		X	X	X		X	X	X	X	
Plasma biomarker sample ^{d,f}		X		X		X		X	X	X		X	X	X	X	
Questionnaire of 6 EIA symptoms ^{d,g}		X		X		X		X ^d		X		X				
Ethanol consumption ^h		X	X			X		X	X							
EIA AEs ⁱ		X	X			X		X	X	X		X	X	X	X	

Abbreviations: AE=adverse event; ECG=electrocardiogram; EIA=ethanol interaction assessment; PK=pharmacokinetics

^a “Time 0” is immediately before the first sip of ethanol is consumed. All Time 0 assessments must be performed prior to initiation of alcohol intake.^b Participants will arrive at the site after a minimum 3-hour fast, then will be provided a standardized meal before receiving the first drink. Participants will be given 30 minutes to consume the meal.^c Catheter placement may be performed earlier in the day if preferred, but participants must be given at least a 20-minute rest period following placement of the venous access catheter prior to recording pre-dose vital signs and ECG. For EIAs conducted prior to a dosing day, the venous catheter will be left in place for PK sample collections.^d If multiple assessments are due at the same timepoint, the order of assessments should be ECG, vitals, blood draw, then any other assessments. The 60-minute symptom assessment should be conducted before the start of the 4th drink.^e To include pulse rate and blood pressure.^f Blood samples will be collected via venous access device. To include acetaldehyde, acetate, and ethanol.^g Participants will be questioned by site staff to assess the 6 symptoms (flushing, headache, lightheadedness, palpitations, nausea, and vomiting) associated with increased blood acetaldehyde levels.^h Ethanol will be consumed in 4 aliquots over an 80-minute period (20 minutes for each aliquot). Time windows do not apply to ethanol consumption. The ethanol will be mixed in a liquid that has no other alcohol, no caffeine, and is low in sugar. The dose of ethanol will be 0.8 g/kg (to a maximum of 56 g) for men and 0.68 g/kg (to a maximum of 48 g) for women. See [Section 8.6.1.3](#) of the protocol for ethanol administration stopping rules.ⁱ AEs associated with administration of ethanol will include events spontaneously reported by participants beginning with the first sip of ethanol (symptoms elicited under direct questioning [footnote g] are not considered AEs).

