4. STUDY DESIGN

4.1. Overall Design

This is a double-blind, randomized, placebo-controlled study of DCR-AUD to evaluate the safety, tolerability, PK, and PD of repeat doses of DCR-AUD in adult HVs.

Each participant will be screened for up to 28 days. Participants may undergo rescreening one time at the discretion of the Investigator or Sponsor. Screening assessments will include a psychological history and a history of alcohol consumption using the TLFB method to identify participants who are HVs and who meet the minimum inclusion/exclusion alcohol consumption requirements. TLFB is a validated method to retrospectively assess drinking behavior history. Randomization and administration of the first dose of study intervention will occur on Day 1.

Repeated doses of 480 mg study intervention will be administered to 16 adult HVs (12 active and 4 placebo). Each participant will receive 3 SC doses of study intervention (on Day 1, Day 29, and Day 57). Up to 10 EIAs will be conducted over the 24-week period to characterize the PD of DCR-AUD.

All participants will be given a diary to track AEs and drinking history for the study duration. Quantitative drinking history will be captured by TLFB questionnaire completed every 2 weeks. Participants will be trained on the use of the diary prior to discharge from the clinic and will report on the diary at each visit.

At the discretion of the Investigator, participants who present with increasing positive ethanol reaction symptoms at the Day 168 EIA (e.g., flushing, headache, lightheadedness, palpitations, nausea, or vomiting) will be followed for an additional 4 weeks (through Day 197).

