5.1. Inclusion Criteria

Participants are eligible to be included in the study only if all the following criteria apply.

Age

1. 21 to 65 years, inclusive, at the time of signing informed consent.

Type of Participant and Disease Characteristics

2. Overtly healthy volunteers, as determined by medical evaluation including medical history, physical examination, and laboratory testing.
3. No diagnosis of AUD within the preceding 12 months per Diagnostic and Statistical Manual of Mental Disorders (DSM-5).
4. Social drinkers who consume, on average, 5 to 20 drinks per week for men or 5 to 14 drinks per week for women over the 4 weeks prior to Screening, and not more than 8 drinks in a single day.
5. No evidence of overt or sub-clinical hepatic pathology, as manifest by serologic tests demonstrating hepatic inflammation or compromised hepatic synthetic function (i.e., AST, ALT, GGT, total bilirubin < 1.5 times the ULN at Screening and Day -1).
6. eGFR \geq 60 mL/min/1.73 m² at Screening.
7. No history of significant adverse reaction(s) to alcohol. Participant should be expected to tolerate the amount of alcohol administered during EIAs.
8. Willing to participate in up to 10 EIAs.
9. Has a negative test for SARS-CoV-2 infection on Day -1.
10. Systolic BP in the range of 80 to 140 mmHg and diastolic BP in the range of 50 to 95 mmHg at Screening. If out of range, BP may be repeated once at the discretion of the Investigator.

Sex and Contraceptive Requirements

11. Male or female
 - Male participants with partners of childbearing potential must agree to use contraception from Screening through at least 24 weeks after the last dose of study intervention and refrain from donating sperm during this period (see [Section 10.4](#)).
 - Female participants may not be pregnant or breastfeeding, and at least one of the following conditions must apply:
 - Is not a woman of childbearing potential (WOCBP) **or**

- If a WOCBP, must agree to follow the contraceptive guidance (see [Section 10.4](#)), beginning at consent and the first Screening visit and for at least 24 weeks after the last dose of study intervention.

Weight

12. BMI within the range 18.0 to 32.0 kg/m² (inclusive).

Informed Consent

13. Capable of giving signed informed consent, which includes compliance with the requirements and restrictions listed in the ICF and in this protocol.

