8.1.1. Alcohol Consumption via Timeline Follow Back

Participants will complete the TLFB at screening and throughout the study period to capture any change in drinking behavior. At every visit, the TLFB will be used to assess each participant's alcohol consumption for the 2-week period that precedes the study visit.

The TLFB was developed as a procedure to aid recall of past drinking ([Sobell & Sobell, 1992](#)). Currently, self-reports are the only viable method for retrospectively measuring drinking with any precision. Alternative methods exist, but they are either impractical (e.g., continuous direct observation), fraught with problems (e.g., alcohol sweat patches), or they only measure very recent drinking (e.g., blood alcohol tests). TLFB stands as the most exhaustively evaluated method that can be used to retrospectively assess drinking behavior over time.

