9.4.4. Exploratory Endpoint(s)

The exploratory endpoint of change in drinking amounts will be assessed using the TLFB and by analysis of blood levels of phosphatidylethanol.

Average daily drinking amounts over each 2-week period after the start of dosing will be compared to the amount during the 2-week period before first dose. Change in drinking amounts for each postdose period will be evaluated in connection with changes in EIA-induced peak symptoms and plasma acetaldehyde levels during the preceding EIA.

Other exploratory analyses will be conducted as deemed appropriate and will be detailed in the SAP.

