4.13.7.2 Exploratory Analyses

The descriptive statistics of participant’s alcohol consumption measured by TLFB will be present for each arm and study days. Each of the drinks will be multiplied by 14g to achieve the alcohol amount. [3]. Change of baseline from both day -1 and screening visit will be presented for each arm. The mean difference and its 95% CI will be presented for the change from baseline of alcohol consumption for each assessment day. Similar analysis will also be performed for total alcohol consumed from baseline.

For PEth descriptive statistics will be present for assessment days. The mean difference and its 95% CI will be presented for the change from baseline of PEth levels for each assessment day.

By participant listings will be present for the exploratory analyses for SP.

4.13.8 Daylight Saving Time (DST):

Not applicable.

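### The two-week TLFB look-back covers half of the four-week eligibility window and, under the schedule after Week 12, leaves three of the twelve post-dose fortnights uncaptured

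*Protocol*

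**What the plan says.** Three places in the protocol fix the look-back at two weeks. Table 1 footnote h says "TLFB will be completed for the 2-week period that precedes each study visit, including Screening". Table 2 footnote m repeats the rule for the non-dosing visits. Section 8.1.1 applies it at every visit, to "alcohol consumption for the 2-week period that precedes the study visit". The SAP's copies of the schedule carry the same footnotes.

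Other sections need more than this:

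- Inclusion criterion 4 (Section 5.1) sets a weekly average "over the 4 weeks prior to Screening, and not more than 8 drinks in a single day".
- Section 4.1 says that Screening includes a "history of alcohol consumption using the TLFB method to identify participants who are HVs" and who meet the alcohol consumption requirements.
- Section 4.1 also says "Quantitative drinking history will be captured by TLFB questionnaire completed every 2 weeks".
- Section 9.4.4 says "Average daily drinking amounts over each 2-week period after the start of dosing will be compared" with the two weeks before the first dose, and relates each period's change to symptoms and acetaldehyde at the preceding EIA.
- SAP 4.13.7.2, after describing change from baseline by assessment day, adds "Similar analysis will also be performed for total alcohol consumed from baseline". It does not say over what period the total runs or how unrecorded days are handled.

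**The concern.** A two-week recall window works only where no more than two weeks need describing. At Screening the criterion spans four weeks. After Week 12 the visits are four weeks apart.

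At Screening, the documents specify no other quantitative tool for criterion 4. Section 2.2.2 relies on participants' drinking histories as evidence that they will tolerate the ethanol given in the EIAs, and Section 5 allows no waivers, so the criterion should be checkable with the data collected.

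In follow-up, the exploratory consumption analysis is promised for each two-week period after dosing starts. If some periods are never recorded, that analysis cannot be produced as written. Its link to the preceding EIA also changes partway through the study, and any cumulative total has holes in it.

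**Working it through.** The documents give no TLFB coverage figure, so there is none to reproduce. The check is a count of nominal days.

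**Inputs**
- Look-back: 14 days (Table 1 footnote h, Table 2 footnote m, Section 8.1.1).
- Eligibility window: 28 days before Screening (inclusion criterion 4).
- Post-dose TLFB visits, first day of each visit: Days 14, 28, 42, 56, 70, 84, 112, 140 and 168. Days 112 and 140 are inferred from Weeks 16 and 20, because the day row of Table 2 is cut off in the text available.
- The Day 168 TLFB rests on Section 8.1.1 (every visit) and the SAP copy of the schedule, because the TLFB row in protocol Table 1 is broken.

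**Eligibility**

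Coverage = 14 / 28 = 50%. The Day -1 TLFB cannot recover the rest. Screening is on Day -2 at the latest, so a 14-day window ending at Day -1 never reaches the third and fourth weeks before Screening.

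The covered fortnight does not settle the criterion. For men the upper limit of 20 drinks per week allows 4 × 20 = 80 drinks in four weeks. A man reporting 20 drinks in the covered fortnight meets that limit if he had 60 or fewer in the other fortnight, and exceeds it at 61 or more. The single-day limit permits up to 14 × 8 = 112 drinks in a fortnight, so it does not rule out the second case.

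**Follow-up**

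Uncovered days between consecutive TLFBs = max(0, interval − 14).

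| TLFB visit | Interval (days) | Post-dose days covered | Days not covered |
|---|---|---|---|
| Day 14 | first | 1–13 | none |
| Days 28, 42, 56, 70, 84 | 14 each | 14–83 | none |
| Day 112 | 28 | 98–111 | 84–97 |
| Day 140 | 28 | 126–139 | 112–125 |
| Day 168 | 28 | 154–167 | 140–153 |

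Covered: 13 + 70 + 3 × 14 = 125 of Days 1–167. Uncovered: 167 − 125 = 42, and 42 / 167 = 25.1%. That is 3 of 12 fortnights, and half of the 84 days from Day 84 to Day 167.

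**Sensitivity**
- Second day of each visit pair (Days 15 to 169): 42 / 168 = 25.0%.
- No TLFB at end of study: 56 / 167 = 33.5%.
- Participants followed to the conditional visit on Day 197, with a TLFB there: 57 / 196 = 29.1%.
- Visit windows, assumed to be ±2 days through the Day 56 visit and ±3 days afterwards (the window rows are partly lost): 38 to 58 uncovered days.
- TLFB every two weeks, as Section 4.1 says: 0 / 167.

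**Link to the EIA**

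Through Day 84 each look-back starts at the preceding EIA; the Day 28 look-back, for example, starts on Day 14. At Day 112 the look-back starts on Day 98, 14 days after the Day 84 EIA. Days 140 and 168 have the same lag.

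**Effect on a total**

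Under constant drinking of *c* per day, a cumulative total records 125*c* of 167*c*, a shortfall of 25%. A total per two-week window loses nothing within that window.

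**The case against.** Four points on the other side deserve weight.

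1. A reader might infer that the SAP's total is 25% too low. The documents do not support that as a fact. SAP 4.13.7.2 never says that the total is cumulative, and the sentences before it work by assessment day, so a total per window is an equally natural reading. Both arms would also share the same gaps.
2. Section 4.1 can be read as removing the gap: it has the TLFB completed every two weeks and gives participants a diary that tracks drinking history. This makes the matter a conflict between sections rather than proof that the days will go unrecorded. It does not resolve the conflict. The schedule has no visit at Weeks 14, 18 or 22, no remote TLFB is described, and Section 8 requires adherence to the schedule. Section 4.1 assigns quantitative history to the TLFB, while the Table 1 footnotes and Sections 8 and 8.6.2 treat the diary as a record of symptoms or adverse events. SAP 4.13.7.2 analyses only TLFB and PEth.
3. A reader might infer that the missing fortnights are those in which drinking is most likely to change, or in which the drug effect is expected. Section 4.2 says only that a sufficient effect may need repeat doses and several months, and it also cites maximum mRNA reduction at four weeks in monkeys. Section 8.1 ties changed intake to symptoms while drinking, not to the fortnight after an EIA. What stands is narrower: the lag between EIA and recorded drinking changes after Day 84.
4. A constant 14-day recall matches the 14-day baseline. Longer recall only at late visits would make recall quality differ by study phase. This stands, and the fix has to allow for it.

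**Conclusion.** The point holds as two inconsistencies.

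First, the Screening TLFB covers 14 of the 28 days in inclusion criterion 4 and cannot verify that criterion by itself. This depends only on the stated windows and affects who is enrolled.

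Second, under the schedule 42 of 167 nominal post-dose days are not captured. Three of the twelve periods in Section 9.4.4 therefore cannot be computed, and Section 4.1 disagrees with the schedule after Week 12. The count assumes nominal days, Days 112 and 140 as inferred, and a TLFB on Day 168. The 25% shortfall in a total is conditional on a cumulative definition and constant drinking.

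The follow-up part bears on one exploratory, descriptive endpoint, for which PEth is a second measure. No primary or secondary analysis is affected. Both parts should be corrected because the correction is cheap, but neither undermines the trial's main objectives.

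**What to change.** - **Screening:** set the look-back to 28 days. For the SAP's change from Screening, use the 14 days nearest the visit so that recall length matches.
- **Day -1 and visits through Day 84:** keep a fixed 14 days. A general rule of looking back to the last TLFB would not work at Day -1, because Screening can be anywhere from 1 to 27 days earlier and the baseline needs two full weeks.
- **Days 112, 140 and 168, and the conditional follow-up visit if a TLFB is done there:** extend the look-back to the previous visit and record it as two 14-day periods. Also report the fortnight nearest the visit alone, so that one series keeps the same recall length as baseline.
- **Alignment:** amend protocol Sections 4.1 and 8.1.1, Table 1 footnote h, Table 2 footnote m and the SAP copies together.
- **SAP 4.13.7.2:** define the total, for example as grams per observed day, and say how unrecorded days are handled.

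With these changes, nominal uncovered days fall from 42 to 0 of 167, and eligibility coverage rises from 14 to 28 of 28 days. The cost is a longer interview at a few visits, with no new visit or sample. Recall for weeks three and four will be poorer, and that loss will fall in the later phase of the study, which is why the nearest fortnight should also be shown separately.
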